**Clinical Study Protocol**  
**Johnson & Johnson Vision**

**CHANGE HISTORY**

Version	Originator	Description of Change(s) and Section Number(s) Affected	Justification for Change	Date
1.0		Original Protocol	N/A	06 October 2022
2.0		
Added AVO MAX 1-Day to list of Keywords on Cover Page
 
Updated Test Article section of Synopsis with correct product names.
 
Section 7.2-V1 Step 1.14 removed wording regarding age of subject as factor in Lens Design Assignment
	Accuracy	12 October 2022
3.0		
Removed the word 'approximately' and the '~' symbol when referencing the total number of subjects for Phase 2.
 
Updated Phase I and Phase II to Phase 1 and Phase 2 throughout for consistency.
 
Updated EDC system name to Clario.
	Accuracy	24 October 2022
4.0		
Increased the planned sample size for Phase 1.
 
Added objective and sample size justification for Phase 1.
 
Clarified sample size calculation for Phase 2 using the data collected from Phase 1.
	To update the planned sample size for Phase 1 and to improve clarity for Phase 2 sample size calculation.	17 March 2023

**Clinical Study Protocol**  
**Johnson & Johnson Vision**

5.0		
Updated endpoints in Section 2.2.
 
Updated hypotheses in Section 2.3
 
Updated statistical Sections 14.2, 14.5, 14.6, and 14.7
 
Updated Phase 2 sample size in Section 4.3 to match synopsis.
 
Updated Section 6.1 CLIFT test article quantities to reflect updated sample size.
	
Based on decision from platform leads based on sample size calculations from Phase 1.
 
Based on decision from platform leads based on sample size calculations from Phase 1.
 
Based on decision from platform leads based on sample size calculations from Phase 1.
 
Accuracy
 
Accuracy
	12 June 2023
-----	--	--	--	--------------

# Clinical Study Protocol

## Johnson & Johnson Vision

### SYNOPSIS

Protocol Title	The Effects of Contact Lenses With UV/HEV-Filter on Visual Function
Sponsor	JJVC, [name]
Clinical Phase	Clinical trial phase: Feasibility Design control phase: 3
Trial Registration	This study will be registered on ClinicalTrials.gov by the Sponsor.
Test Article(s)	Investigational Products: senofilcon A-based contact lens (toric) with new UV/HEV filter Approved Products: ACUVUE® OASYS MAX 1-Day (sphere, multifocal), ACUVUE® OASYS 1-Day (sphere, toric), ACUVUE® OASYS Multifocal
Wear and Replacement Schedules	Wear Schedule: Daily wear Replacement Schedule: Daily
Objectives	The objectives of this study are to objectively measure potential benefits of a new UV/HEV filter using psychophysical testing techniques.
Study Endpoints	Primary endpoint(s): visual range Secondary endpoint(s): brightness perception, motion detection Other observations: Ocular physiology.
Study Design	
This is a 2-phase, single-site, non-dispensing, randomized, controlled, double-masked, 2x2 crossover study. There will be 2 subject groups (sphere wearers and multifocal wearers) in Phase 1 and 3 subject groups (sphere wearers, multifocal wearers, and toric wearers) in Phase 2. Each subject will be bilaterally fitted with one of the two test articles in each of the two periods within each study phase.
 
There will be a total of 2 visits in each phase of the study:
 

1. Visit 1: Screening, baseline evaluation, lens fit #1 and psychophysical evaluation

2. Visit 2: Baseline evaluation, lens fit #2, psychophysical evaluation, and final evaluation.

 
See the flow chart at the end of the synopsis table for the schematic of the study visits and procedures of main observations (Figure 1).

# **Clinical Study Protocol**

## **Johnson & Johnson Vision**

Sample Size	
Phase 1 will pilot the procedures and will enroll approximately 24 subjects, with a target of at least 20 to complete (~10 spherical wearers and ~10 multifocal wearers). Data from Phase 1 will be used for sample size estimation for Phase 2. Subjects in Phase 1 will not participate in Phase 2.
 
Phase 2 will execute the same procedures as Phase 1 with a different sample size. Phase 2 sample size will be calculated based on data collected from Phase 1. The total sample size for Phase 2 will be approximately 135 subjects (45 per subject group to enroll and 40 to complete) due to resources and study timing.

Study Duration	
There are two study visits in each phase that will last approximately 2.5-3 hours each and will be separated by 1-14 days.
 

• The study enrollment period for Phase 1 will be approximately 2 weeks, making the duration of Phase 1 approximately 4 weeks.

• Up to 2 weeks will be allotted for statistical analyses.

• The study enrollment period for Phase 2 will be approximately 12 weeks, making the duration of Phase 2 approximately 14 weeks.

• The total study duration is expected to last about 20 weeks.

Anticipated Study Population	
All subjects will be healthy adult male and female volunteers of any race and ethnicity that satisfy the inclusion criteria. All subjects must habitually wear one of three soft contact lenses within the power ranges available for this study:
 

1. Spherical

2. Multifocal

3. Toric (astigmatism)

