#### Primary Objective(s)

The primary objective of Phase 1 study is to collect clinical data to estimate the required Phase 2 sample size for achieving the primary objective with adequate statistical power given the prespecified primary hypotheses testing.

The primary objective of the Phase 2 study is to objectively measure potential benefits of a new UV/HEV filter using psychophysical testing techniques.

The results from this study may be used to support marketing claims or help understand market readiness of the Test lenses that contain the UV/HEV filter.

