### **4.3. Enrollment Target and Study Duration**

#### Phase 1

Phase 1 will have an enrollment target of 24 subjects, with a target of at least 20 to complete. Approximately 10 subjects will wear spherical soft contact lenses and approximately 10 subjects will wear multifocal soft contact lenses. The study will be conducted at a single clinical site. A subject will be considered enrolled upon signing the informed consent form.

There will be 2 visits in total per subject separated by 1-14 days. The enrollment period is 2 weeks making the duration of Phase 1 approximately 4 weeks. If subjects discontinue prior to the final evaluation, then additional subjects may be enrolled at the discretion of the study sponsor to maintain sample size requirements.

#### Phase 2

Phase 1 results are used to estimate the number of subjects required for Phase 2. However, the total sample size for Phase 2 will be approximately 135 subjects due to resources and study timing. The study will be conducted at a single clinical site. A subject will be considered enrolled upon signing the informed consent form. Phase 1 subjects will not be Phase 2 subjects.

There will be 2 visits in total per subject separated by 1-14 days. The enrollment period is 12 weeks making the duration of Phase 2 approximately 14 weeks. If subjects discontinue prior to the final evaluation, then additional subjects may be enrolled at the discretion of the study

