### **14.2. Sample Size Justification**

Sample size for Phase 1 was not determined on the basis of statistical considerations because it is primarily for the collecting clinical data to calculate the required sample size for Phase 2.

Sample size requirements for Phase 2 were based on assumptions derived from the analysis of selected data collected in Phase 1. It was calculated that the total sample size of 120 subjects to complete (40 per group) the study provides at least 90% power to test each primary and secondary hypothesis. The sample size and power calculations were performed using a paired sample *t*-test approach (exact method) in PASS (NCSS, 2021).

A gate-keeping approach will be used to control the study-wise Type I error rate at the one-sided 0.025 level and adjust for multiplicity due to multiple efficacy endpoints of interest in combination of Bonferroni adjustment. The null hypothesis for the primary efficacy endpoints has to be rejected at one-sided alpha level of 0.025 first, in order to propagate the full alpha to the secondary family of hypothesis tests. The Bonferroni approach will apply then to testing the secondary efficacy endpoints.

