# Clinical Study Protocol

## Johnson & Johnson Vision

The sample size estimates for primary endpoints were calculated using 1-sided Type I error rate of 0.025 for each endpoint. The sample size estimates for the two secondary endpoints were adjusted using a Bonferroni adjustment and calculated using a one-sided Type I error rate of 0.0125 (i.e., one-sided 0.025/2).

While no Toric wearers were enrolled in Phase 1, it is anticipated that the multifocal group would require the largest sample due to simultaneous optics of the multifocal lens and the intraocular scattering that naturally occurs with age, which can both compromise and reduce the quality of vision. Hence it is expected that the sample size required to test endpoints for Toric wearers would be no more than the sample size required for Multifocal wearers. As these endpoints did not have data from Phase 1, all hypotheses for the Toric wearers will be exploratory endpoints.

Table 9 displays the statistical power and associated sample sizes estimates derived for the primary and secondary endpoints for Sphere and Multifocal groups, given the assumed treatment effect sizes. Based on the table below, it is planned that Phase 2 will enroll approximately 135 subjects (45 subjects per group) with the target of 120 subjects (40 subjects per group) to complete the study, assuming approximately a 10% drop-out rate.

Table 9: Assumptions for Power and Sample Size Calculations for The Primary and Secondary Endpoints

Endpoint Type	Endpoint (Subject Group)	Standard Deviation of Paired Differences	Effect Size	Alpha	Power	Sample Size Per Group
Primary	Visual Range (Sphere)	0.10	1.83	0.05	0.94	6
	Visual Range (Multifocal)	0.23	0.52	0.05	0.90	41
Secondary	Motion Detection (Sphere)	1.16	0.99	0.03	0.92	16
	Brightness Perception (Multifocal)	0.20	0.70	0.03	0.91	29

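### Equal groups of 40 leave the multifocal primary at 0.894 power, just under the stated 90%, while both tested sphere endpoints exceed 0.999; moving a few places would correct this within the same total

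*Combined protocol and SAP*

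**What the plan says.** Section 2.1 gives Phase 1 the task to "collect clinical data to estimate the required Phase 2 sample size for achieving the primary objective with adequate statistical power". Section 14.2 then reports the result for Phase 2: "It was calculated that the total sample size of 120 subjects to complete (40 per group) the study provides at least 90% power", for all primary and secondary tests. It turns this into group sizes: "Phase 2 will enroll approximately 135 subjects (45 subjects per group) with the target of 120 subjects (40 subjects per group", allowing for about 10% drop-out. The synopsis gives the same equal split: "The total sample size for Phase 2 will be approximately 135 subjects (45 per subject group to enroll and 40 to complete".

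Table 9 lists different needs by group. Sphere wearers need 6 for visual range (primary) and 16 for motion detection (secondary). Multifocal wearers need 41 for visual range (primary) and 29 for brightness perception (secondary). The text of section 14.2 also expects the multifocal group to need the most subjects. Toric wearers had no Phase 1 data, and their hypotheses are exploratory.

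Section 4.3 explains the total: "the total sample size for Phase 2 will be approximately 135 subjects due to resources and study timing". No section explains why the total is divided equally. Section 5.1 stratifies randomization by subject group, and sections 14.4 and 14.5 test and model the groups separately. Section 14.4 allows a secondary test only if the primary of the same group succeeds. Section 14.8 sets a lower bar, 80% power for each group's primary, and mentions a maximum of about 150 subjects.

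**The concern.** The common figure of 40 is one below Table 9's own requirement for the multifocal primary and 2.5 times the largest requirement listed for sphere wearers (40/16). Neither the randomization nor the analysis needs equal groups. On the plan's assumptions, nearly all the risk of a failed primary therefore sits in the multifocal group. A failure there also closes the gate on multifocal brightness. At stake are the accuracy of the power statement in section 14.2 and some power in the weakest primary that could be had without enrolling anyone extra.

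**Working it through.** **Inputs.** Effect sizes d (mean difference divided by the SD of paired differences) come from Table 9: sphere visual range 1.83, multifocal visual range 0.52, sphere motion 0.99, multifocal brightness 0.70. The test is the paired t-test, described in section 14.2 as an "approach (exact method) in PASS" calculation. For the primaries, "The sample size estimates for primary endpoints were calculated using 1-sided Type I error rate of 0.025 for each endpoint"; the secondaries were "calculated using a one-sided Type I error rate of 0.0125 (i.e., one-sided 0.025/2". The 0.05 and 0.03 printed in Table 9 are the two-sided equivalents, the latter rounded. Reading 0.05 as one-sided would give 0.984 and 0.948 for the two primaries, which does not match the table.

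**Formula.** Power = P(T > t(1−α, n−1)), where T is noncentral t with n−1 degrees of freedom and noncentrality d√n.

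**Step 1: reproduce Table 9.**

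| Endpoint | n | d√n | Critical t | Computed | Table 9 |
|---|---|---|---|---|---|
| Sphere visual range | 6 | 4.483 | 2.571 | 0.943 | 0.94 |
| Multifocal visual range | 41 | 3.330 | 2.021 | 0.901 | 0.90 |
| Sphere motion | 16 | 3.960 | 2.490 | 0.916 | 0.92 |
| Multifocal brightness | 29 | 3.770 | 2.368 | 0.912 | 0.91 |

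All four agree.

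**Step 2: multifocal visual range at the planned 40.** Noncentrality is 0.52 × √40 = 3.289 and critical t is 2.023, so power is 0.894. If 0.52 is a rounded value between 0.515 and 0.525, power lies between 0.888 and 0.899. Using n−2 degrees of freedom for the crossover gives 0.893.

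**Step 3: the gate.** Multifocal brightness alone has 0.979 at 40. If the two endpoints are independent, the chance of passing both tests is 0.894 × 0.979 = 0.875. Positive correlation would raise this, but never above 0.894.

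**Step 4: move five completers, toric held at 40.**

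| Sphere / multifocal completing | Multifocal visual range | Brightness alone | Brightness after gate | Sphere visual range | Sphere motion |
|---|---|---|---|---|---|
| 40 / 40 | 0.894 | 0.979 | 0.875 | >0.9999 | 0.9999 |
| 35 / 45 | 0.927 | 0.990 | 0.917 | >0.9999 | 0.9997 |

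The failure risk of the multifocal primary falls from 10.6% to 7.3%.

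**Step 5: smaller true effects.** The Table 9 effects come from about 10 completers per group. With every d multiplied by 0.6, the move from 40/40 to 35/45 takes sphere motion from 0.918 to 0.873 (−0.045) and multifocal visual range from 0.486 to 0.535 (+0.049). The product of all four powers, which is the chance of all four claims under independence, rises from 0.875 to 0.917 at Table 9 effects. At half those effects it rises from 0.130 to 0.148.

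**Step 6: period-1 fallback.** Sections 14.5 and 14.6 use only period 1 if the sequence effect is significant. The comparison is then between subjects, with standardized effect d√(2(1−ρ)) under equal variances. The within-subject correlation ρ is not given, so 0.3, 0.5 and 0.7 are assumed. Going from 20 versus 20 to 17 versus 18, sphere motion falls from 0.91 to 0.86, 0.78 to 0.72 and 0.54 to 0.48. Going from 20 versus 20 to 22 versus 23, multifocal visual range rises from 0.47 to 0.52, 0.36 to 0.40 and 0.24 to 0.26.

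**The case against.** The strongest defence is that no requirement is materially missed. The shortfall is one subject, power is well above the 80% in section 14.8, and all 45 enrolled would give 0.927 if every one completed. Sections 4.3 and 8.2 also provide for replacing drop-outs. This stands as a limit on severity. It does not make the statement in section 14.2 correct, because that statement is made for 40 completers.

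A reader might infer that the plan disregards Phase 1. The documents do not support that: section 14.2 ties enrolment to Table 9, and 40 tracks the largest listed need. Sizing every group to the most demanding one is a recognized conservative choice.

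A reader might also infer that a larger shift, such as 30 sphere and 50 multifocal, is nearly free and should be required. Under Table 9 it would give 0.950 for multifocal visual range and 0.998 for sphere motion. At 60% of those effects, however, it costs sphere motion 0.110 (0.918 to 0.808) against a multifocal gain of 0.094 (0.486 to 0.580). With about 10 pilot subjects, the 95% interval around d = 0.99 for sphere motion runs from roughly 0.21 to 1.74, so some sphere surplus is a reasonable buffer.

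Two further points stand. The documents give no recruitment figures by group, so resources and timing may limit the multifocal group as well as the total. The ceiling of about 150 in section 14.8 would also allow multifocal subjects to be added without taking any from sphere: 41 completers need 41/0.9 = 45.6, so 46 enrolled.

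**Conclusion.** The point holds as one of efficiency, with a marginally overstated power. At 40 completers multifocal visual range has 0.894 power (0.888 to 0.899 over the rounding of d) against a stated minimum of 0.90, while both tested sphere endpoints exceed 0.999. The other three tests meet 0.90 when taken alone. The 0.875 for brightness is a gated figure that assumes independence, and section 14.2 does not say that its powers allow for the gate.

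A reader might infer that the trial is underpowered or its analysis invalid. Neither follows: type I error, bias and validity are untouched, and the 80% target is met under Table 9 assumptions. All of this depends on effect sizes from a small pilot, on the paired t approximation to the planned mixed model, on both periods being used, and on the within-group gate of section 14.4.

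**What to change.** Keep about 135 enrolled and 120 completing. In the synopsis, section 4.3 and section 14.2, replace the equal split with group targets, for example 35 sphere, 45 multifocal and 40 toric completers. At 10% drop-out, enrolment is 35/0.9 = 38.9, so 39; 45/0.9 = 50; and 40/0.9 = 44.4, so 45; a total of 134. Update the randomization list length in each stratum and the lens quantities in section 6.1. If the split must stay equal, give the reason and restate the section 14.2 power for multifocal visual range as about 89%.

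The costs are about five more presbyopes to recruit at one site in 12 weeks, slightly less precision in the sphere group, and less sphere-motion margin if true effects are much smaller or the period-1 fallback is used. A shift as large as 30/50 is a trade-off for the sponsor to weigh, not a required change.

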# **Clinical Study Protocol**

## **Johnson & Johnson Vision**

Eligibility Criteria - Inclusion	
Potential subjects must satisfy all of the following criteria to be enrolled in the study:
 
Inclusion Criteria following Screening The subject must:
 

1. Read, understand, and sign the STATEMENT OF INFORMED CONSENT and receive a fully executed copy of the form.

2. Appear able and willing to adhere to the instructions set forth in this clinical protocol.

3. Be between 18 and 70 (inclusive) years of age at the time of screening.

4. By self-report, habitually wear soft contact lenses (sphere, multifocal, toric) in both eyes in a daily reusable or daily disposable wear modality (i.e. not extended wear modality). Habitual wear is defined as a minimum of 6 hours of wear per day, for a minimum of 5 days per week during the past 30 days.

 
Inclusion Criteria at Baseline Evaluation
 

5. If applicable, those subjects receiving the spherical lenses will need a vertex-corrected distance refraction within the range of -1.00 through -6.00 DS

6. If applicable, those subjects receiving the multifocal lenses will need a vertex-corrected distance refraction within the range of -1.00 through -6.00 DS

7. If applicable, those subjects receiving the toric lenses will need a vertex-corrected distance refraction within the range of -1.50 through -4.00 DS, -0.625 through -1.625 DC, and cylinder axes: 80/90/100, 170/180/10

8. The best corrected, monocular, distance visual acuity must be 20/25 or better in each eye.

----------------------------------	--

# **Clinical Study Protocol**

## **Johnson & Johnson Vision**

[figure not shown]
Eligibility Criteria – Exclusion	
Potential subjects who meet any of the following criteria will be excluded from participating in the study:
 
Exclusion Criteria following Screening The subject must not:
 

1. Be currently pregnant or lactating.

2. Be currently using any ocular medications or have any ocular infection of any type.

3. By self-report, have any ocular or systemic disease, allergies, infection, or use of medication that the investigator believes might contraindicate or interfere with contact lens wear, or otherwise compromise study endpoints, including infectious disease (e.g., hepatitis, tuberculosis), contagious immunosuppressive disease (e.g., Human Immunodeficiency Virus [HIV]), autoimmune disease (e.g. rheumatoid arthritis, Sjögren's syndrome), or history of serious mental illness or seizures. See section 9.1 for additional details regarding excluded systemic medications.

4. Have habitually worn rigid gas permeable (RGP) lenses, orthokeratology lenses, or hybrid lenses (e.g. SynergEyes, SoftPerm) within the past 6 months.

5. Be currently wearing lenses in an extended wear modality.

6. Have participated in a contact lens or lens care product clinical trial within 14 days prior to study enrollment.

7. Be an employee (e.g., Investigator, Coordinator, Technician) or immediate family member of an employee (including partner, child, parent, grandparent, grandchild or sibling of the employee or their spouse) of the clinical site.

8. (Phase 2 only): Have participated in Phase 1 of the study.

 
Exclusion Criteria at Baseline Evaluation The subject must not:
 

9. Have clinically significant (grade 3 or higher on the FDA grading scale) slit lamp findings (e.g., corneal edema, neovascularization or staining, tarsal abnormalities or bulbar injection) or other corneal or ocular disease or abnormalities that the investigator believes might contraindicate contact lens wear or may otherwise compromise study endpoints (including entropion, ectropion, chalazia, recurrent styes, glaucoma, history of recurrent corneal erosions, aphakia, moderate or above corneal distortion, herpetic keratitis).

10. Have a history of strabismus or amblyopia.

----------------------------------	--

**Clinical Study Protocol**  
**Johnson & Johnson Vision**

	
11. Have fluctuations in vision due to clinically significant dry eye or other ocular conditions.
 
12. Have had or have planned (within the study period) any ocular or intraocular surgery (e.g., radial keratotomy, PRK, LASIK, iridotomy, retinal laser photocoagulation, etc.).

Disallowed Medications/Interventions	
No ocular medications.
 
See section 9.1 for details regarding disallowed systemic medications.

Measurements and Procedures	
The new UV/HEV-filter has the potential to provide visual benefits that go beyond the correction of ametropia. To evaluate some of these benefits, various laboratory equipment will be used to measure visual range, brightness perception, and motion detection in accordance with published literature and established psychometric and psychophysical principles.

Microbiology or Other Laboratory Testing	None
Study Termination	
The occurrence of an Unanticipated Adverse Device Effect (UADE) or Serious Adverse Event (SAE) for which a causal relationship to a test article cannot be ruled out, will result in stopping further dispensing investigational product. In the event of a UADE or SAE, the Sponsor Medical Monitor may unmask the treatment regimen of subject(s) and may discuss this with the Principal Investigator before any further subjects are enrolled.

Ancillary Supplies/ Study-Specific Materials	
Optical device for measuring visual range; light track for motion detection, projected optics for measuring brightness perception.

Principal Investigator(s) and Study Institution(s)/Site(s)	
A full list of Principal Investigators, clinical sites, and institutions is kept separately from the Study Protocol and is included in the study Trial Master File.

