#### **5.2. Masking**

This is a double-masked study. Subjects will be unaware of the identity of the investigational product. The investigator conducting the psychophysical testing will also not be informed. Instead, lens type will be identified by code only, and the link between the code and the lens type will not be revealed to the investigator conducting the psychophysical testing until after the database has been locked. The clinician fitting the lenses will not be masked as to the identity of the investigational products and may be able to tell the difference between the Test and Control lenses based on color differences between the lenses.

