**Clinical Study Protocol**  
**Johnson & Johnson Vision**

Visit 1: Treatment 1 Lens Fitting		
Step	Procedure	Details
1.43	Continuance	
For the subject to continue in the study, they must meet all three of the following criteria:
 
 
• Distance visual acuity is 20/30 or better OD and OS.
 
• The lens fit is acceptable OD and OS.
 
• Investigator approval.
 
 
If the Investigator does not approve the dispensing of the first study lens, then the study is terminated for that subject.

1.44	Lenses Worn in Clinic	
The lenses will be released for approximately 2.5 hours for psychometric testing.
 
 
1. The subjects must wear both study lenses the entire time.
 
2. The lenses will be worn as daily wear only.
 
3. Rewetting drops are permitted if needed.
 
 
Note: In the event a lens is lost or damaged, it will be replaced immediately.

1.45	Psychophysical Testing Sequence	
The following psychophysical tests will be performed in any order:
 
 
1. Visual range (OU) at approximately 8 cpd 
 
a. Units: log relative energy
 
b. Range / decimal places: 0.00-10.00
 
 
 
2. Brightness perception (OU) 
 
a. Units: log relative energy
 
b. Range / decimal places: 0.00 to 10.00
 
 
 
3. Motion detection (OU) 
 
a. Units: mm
 
b. Range / decimal places: 0.00 – 700.00
 
 
 
 
Following the psychophysical testing by the principal investigator, the subject will return to the sub-investigator.

1.46	Lens Removal	The worn study lenses will be removed and discarded.

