## **Clinical Study Protocol** **Johnson & Johnson Vision**

suspended. Upon review and consultation with IRB, and JJVC Safety Review committee, the study may be terminated.

The occurrence of one or more Unanticipated Serious Adverse Device Effect (USADE), or any SAE where the relationship to study agent cannot be ruled out, may result in stopping further dispensing of test article. In the event of a USADE or SAE, the Sponsor may unmask the treatment regimen for the subject(s) and will discuss this with the Investigator before any further subjects are enrolled.

The Sponsor will determine when a study will be stopped. The Principal Investigator always has the discretion to initiate stopping the study based on patient safety or if information indicates the study's results are compromised.

JJVC reserves the right to terminate the study at any time for any reason. Additionally, the IEC/IRB reserves the right to terminate the study if an unreasonable risk is determined. The study can be terminated by the Principal Investigator at the individual clinical site due to specific clinical observations, if in their opinion, after a discussion with JJVC, it is determined that it would be unwise to continue at the clinical site.

JJVC (and the IEC/IRB and DMC, if applicable) will evaluate all adverse events. If it is determined that an adverse event presents an unreasonable risk, the investigation, or that part of the investigation presenting the risk, will be terminated as soon as possible.

Should the study be terminated (either prematurely or as scheduled), the Investigator will notify the IEC/IRB and Regulatory Authority as required by local regulatory requirements.

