## **Clinical Study Protocol Johnson & Johnson Vision**

When medically necessary, the Investigator may break the randomization code to determine the identity of the treatment that the subject received. The Sponsor and study monitor should be notified prior to unmasking the test articles.

In the event of a serious/significant adverse event, the Investigator must:

- Notify the Sponsor immediately.
- Obtain and maintain in the subject's records all pertinent medical information and medical judgment for colleagues who assisted in the treatment and follow-up of the subject.
- Provide the Sponsor with a complete case history which includes a statement as to whether the event was or was not related to the use of the test article.
- Notify the IEC/IRB as required by the IEC/IRB reporting procedure according to national regulations.

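### A safety unmasking may be discussed with the principal investigator, who is also the tester that Section 5.2 keeps masked until database lock

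*Combined protocol and SAP*

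**What the plan says.** **Masking of the tester.** Section 5.2 states: "The investigator conducting the psychophysical testing will also not be informed". It adds that "the link between the code and the lens type will not be revealed to the investigator conducting the psychophysical testing until after" database lock. The same section says that the clinician who fits the lenses is not masked.

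**Who the tester is.** Step 1.45 reads: "Following the psychophysical testing by the principal investigator, the subject will return to the sub-investigator". Step 2.34 says the same for Visit 2. The tests are visual range (primary), brightness perception and motion detection.

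**Who may be told.** The synopsis, under Study Termination, says that after a UADE or SAE "the Sponsor Medical Monitor may unmask the treatment regimen of subject(s) and may discuss this with the Principal Investigator". Section 11 says that "the Sponsor may unmask the treatment regimen for the subject(s) and will discuss this with the Investigator before any further subjects are enrolled". Section 13.4.1 adds that, where medically necessary, "the Investigator may break the randomization code to determine the identity of the treatment that the subject received".

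**General unmasking rules.** Section 5.3 gives the decode to the unmasked biostatistician and the medical monitor. It confines mask-breaking before study end to emergencies in which knowing the assignment would decide the subject's care, and it requires a record of when and why the mask was broken. It advises the investigator against passing the assignment on, and it expects the unmasked subject to attend the remaining visits.

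**The concern.** The synopsis names, as a possible recipient of unmasked information, the one person at the site whom Section 5.2 protects from it. The fitting clinician is unmasked already and could receive the same information without loss.

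At stake is assessor masking for the primary endpoint. Section 1, A.6 has the researcher raise the haze step by step until the grating can no longer be resolved, so the tester paces the measurement. Section 15.1 also has the tester do calculations on paper before data entry. A tester who knows the lens could shift the result without meaning to, and the claim of double masking would be weaker for any subject tested after that point.

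**Working it through.** The plan gives no figure on this point, so the first three steps compare texts. The fourth is an illustration.

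**1. Do the rules conflict?** The tester is the principal investigator (steps 1.45 and 2.34), and the tester must not learn the link before lock (5.2). The synopsis lets the medical monitor unmask and discuss this with the principal investigator. These cannot both be followed if the discussion includes the lens identity. Section 5.3 does not resolve this. Its advice covers onward disclosure by the investigator, not disclosure to the tester. It names no substitute tester, and Section 14 does not say how data collected after an unmasking are analysed. The emergency limit in 5.3 is absent from the synopsis and Section 11.

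**2. How far would one unmasking reach?** In a 2x2 crossover, knowing one period's lens reveals the other, so that subject is fully decoded. Reach beyond that subject depends on the codes. Section 5.2 ties a code to lens type, and the pack contents listed in 5.3 include randomization codes but no subject number. This suggests shared codes, but the number of codes per lens is not stated. Section 6.4 says the sample labels are not representative, so they cannot settle it.

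Assume k equally used codes per lens. A later subject in the same group is decodable if either of that subject's two codes matches one already revealed, so the share is 1 − (1 − 1/k)²:

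- k = 1: 100%
- k = 2: 75%
- k = 3: 56%
- k = 4: 44%
- codes unique to each subject: no later subject

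For an event a quarter of the way through one group of 45 (assumed timing) and k = 1, the later subjects number 45 × 0.75 = 33.75, about 34.

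**3. Would testing continue?** The synopsis says that an event whose causal link to a test article cannot be excluded *will* stop further dispensing. Section 11 says that such an event *may* stop it. Both unmasking sentences look ahead to further enrolment. The documents do not settle the matter, and the two passages must be reconciled.

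**4. What could a tester shift do?** The inputs are from Table 9 and Section 14.4: multifocal visual range, SD of paired differences 0.23, effect size 0.52, one-sided alpha 0.025. Power is 1 − F(t(1−α, n−1)), where F is the noncentral t distribution with n − 1 degrees of freedom and noncentrality δ√n. With n = 41 and δ = 0.52 this gives 0.901, which reproduces the 0.90 in Table 9.

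Now let the true difference be zero, n = 40 completers, and a share f of subjects be tested with a shift b in favour of Test. Hold the SD at 0.23, so δ = f × b / 0.23. For example, 0.5 × 0.05 / 0.23 = 0.109. The rejection probabilities are:

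| Assumed shift b (LRE) | f = 0.25 | f = 0.5 | f = 1 |
|---|---|---|---|
| 0.02 | 0.034 | 0.045 | 0.077 |
| 0.05 | 0.052 | 0.099 | 0.268 |

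The planned level is 0.025. For scale, Table 9 implies differences of 0.52 × 0.23 = 0.12 LRE (multifocal) and 1.83 × 0.10 = 0.18 LRE (sphere). A shift of 0.05 is 42% and 27% of these. No document gives a size for b.

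**The case against.** **Unmasking is optional.** The synopsis says *may* twice. Only Section 11 makes the discussion definite, and only once an optional unmasking has taken place. Neither passage says that the code link must be handed over. This stands. It makes the event rarer but leaves the conflict in place.

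**Sections 11 and 13.4.1 say Investigator, not principal investigator.** Elsewhere that word also covers the person fitting lenses, and Section 11 uses Principal Investigator separately. Those two passages could be read as reaching the unmasked fitter. This also stands, but the synopsis is explicit, and an ambiguous recipient is itself a reason to reconcile the texts.

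**Section 5.3 already limits and documents unmasking.** It does, so recording the date is not a new requirement. It does not shield the tester.

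**The subject stays masked.** Brightness is set by the subject with a wedge, motion is judged from a motor-driven light, and the visual range trial ends on the subject's own report. The bias route is therefore clearest for visual range and less direct for the other two measures.

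**A stronger reading is tempting:** that one safety event unmasks the assessor of every endpoint for the rest of the study, or for about 135 × 0.75 = 101 subjects. The documents do not support it. It needs codes shared across all three lens groups, no re-coding, and testing that continues after the event. None of these is stated.

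**Conclusion.** The conflict between the synopsis and Sections 5.2 and 11 is real, and nothing elsewhere in the protocol removes it. Its practical weight is small to moderate because it depends on an unmasking that is optional and probably rare: wear is 2.5–3 hours per visit, and two of the three test lenses are marketed.

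If an unmasking happens, the certain reach is one subject's two lens assignments, and only measurements not yet taken can be affected. Reach to later subjects, about 34 in the example, rests on shared codes, an early event and continued testing. The type I error figures rest on an assumed shift and show sensitivity, not an expected effect. Confidence is high on the contradiction and moderate on its reach. This is a cheap improvement, not a flaw that undermines the design.

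**What to change.** 1. In the synopsis and Section 11, direct non-emergency discussion of unmasked lens identity to the medical monitor and the fitting clinician, who is unmasked under 5.2. That this clinician is the sub-investigator is inferred from 5.2 and step 1.45, so name the role. Give the principal investigator the event and the sponsor's decision, without the lens identity or code link.
2. Leave medically necessary unmasking under 5.3 and 13.4.1 as it is. Reconcile those sections with the synopsis, 5.2 and 11, including who is meant by Investigator and the *will*/*may* difference on dispensing.
3. State the code structure: how many codes per lens, and whether they are shared across subjects or groups.
4. In Section 14.5, add that if the tester becomes unmasked, the primary analysis is repeated as a sensitivity analysis on data collected before the unmasking date, which 5.3 already requires to be documented.

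The cost is wording only, with no extra staff. The one downside is that the principal investigator would discuss a non-emergency safety pause without knowing the lens identity.
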